6. Sample Size Calculation

Sample size estimation was based on prior findings by Reddy et al., where the PPC rate was 54% in smokers and 16% in nonsmokers. With a power of 90% and a significance level of 5%, the required sample size was calculated to be 62 participants per group. To account for a potential 10% data loss due to dropouts or missing data, the final target sample size was adjusted to 70 participants

7. Data Collection Methods

Demographic data (age, gender, BMI), smoking status, intraoperative variables (FiO₂, PEEP, Ppeak, duration of surgery), and postoperative respiratory findings (cough, secretion, wheezing, SpO₂) will be recorded using a standardized case report form. Observations will be made at 6 and 24 hours postoperatively.

8. Outcome Measures

Primary Outcome:

- Incidence of PPCs within 24 hours postoperatively

Secondary Outcomes:

- Frequency of suctioning
- VAS score for cough severity at 6 and 24 hours

- Presence of wheezing, laryngospasm, SpO2 <90%
- Need for respiratory physiotherapy
- Length of PACU stay

9. Statistical Analysis Plan

Descriptive statistics will include means and standard deviations for continuous variables (or medians and interquartile ranges, depending on distribution) and frequencies/percentages for categorical variables.

Normality will be assessed with the Shapiro-Wilk test.

Between-group comparisons will be made using:

- Independent t-test or Mann-Whitney U test for continuous variables
- Chi-square or Fisher's exact test for categorical variables

Multivariate logistic regression analysis will be used to determine independent predictors of PPCs. Adjusted odds ratios (aORs) with 95% confidence intervals (CIs) will be reported.

Receiver Operating Characteristic (ROC) curve analysis will assess predictive performance of continuous variables like Ppeak or BMI. Area under the curve (AUC), cut-off values, sensitivity and specificity will be provided.

Sensitivity analyses will include subgroup comparisons. A post-hoc power analysis will confirm statistical adequacy based on observed effect sizes.

10. Ethical Considerations

This study was approved by the Clinical Research Ethics Committee of Gazi Yasargil Training and Research Hospital (Approval No: 257, Date: 07.02.2025). All participants will provide written informed consent.

11. Contact Information

Principal Investigator:

[name] [name]

Specialist in Anesthesiology and Reanimation
Gazi Yasargil Training and Research Hospital

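### Post-hoc power at the observed effect restates the p-value, so it cannot confirm that the sample was adequate

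*Combined protocol and SAP*

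**What the plan says.** Section 8 makes the primary outcome "Incidence of PPCs within 24 hours postoperatively", a yes/no outcome per patient. For such outcomes Section 9 plans "Chi-square or Fisher's exact test for categorical variables", followed by a multivariable logistic regression whose adjusted odds ratios come with 95% confidence intervals. The section closes with: "A post-hoc power analysis will confirm statistical adequacy based on observed effect sizes".

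Section 9 names no outcome for this power analysis, no threshold for adequacy and no rule for using the result.

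The prospective calculation is separate, in Section 6. It rests on an earlier study "where the PPC rate was 54% in smokers and 16% in nonsmokers", with 90% power and a 5% significance level. It states that "the required sample size was calculated to be 62 participants per group" and, after a 10% allowance for loss, that "the final target sample size was adjusted to 70 participants", without saying whether 70 is per group or in total. Section 9 does not tie the post-hoc calculation to the Section 6 rates.

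**The concern.** Whether a sample was adequate depends on an effect chosen independently of the data, or on how precisely the effect was estimated. Power at the observed effect addresses neither. It takes the estimate as the truth and asks how often the same test would reject, and the p-value has already settled that. The plan nevertheless says in advance that the figure will confirm adequacy.

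Two misreadings follow. A null or modest result would be labelled underpowered even if the design had ample power for its planning effect. A clearly significant result would be taken as proof that the sample was large enough.

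An interval for the primary comparison would inform the reader, but Section 9 promises intervals only for the adjusted odds ratios. The crude comparison of incidence, which is the primary objective in Section 2, gets a test with no stated effect measure or interval.

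**Working it through.** **Inputs.** Rates of 54% and 16%, so a planning difference of 54 - 16 = 38 points; 90% power; 5% significance; 62 per group; target 70 (all Section 6). Chi-square or Fisher test (Section 9). *Assumptions:* two-sided testing, since the plan does not state sidedness, and equal groups. The event counts in step 3 are hypothetical.

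**1. The plan's own sample size.** With pooled rate (0.54 + 0.16)/2 = 0.35:

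n per group = [1.960 × √(2 × 0.35 × 0.65) + 1.282 × √(0.54 × 0.46 + 0.16 × 0.84)]² / 0.38² = 30.98, so 31 per group.

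The stated 62 per group does not reproduce; 2 × 31 = 62 matches it as a total. Other versions do not reach it either: 37 with continuity correction, 28 unpooled, 31 arcsine. That belongs to Section 6, and the point here does not depend on it. Both sizes are carried forward: 62 per group, and 35 per group if 70 is the total.

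Power at 54% vs 16%, using Φ[(difference - 1.96 × SE under the null) / SE under the alternative]:

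| n per group | Normal approximation | Exact chi-square | Exact Fisher |
|---|---|---|---|
| 31 | 0.900 | – | 0.851 |
| 35 | 0.933 | 0.937 | 0.900 |
| 62 | 0.997 | 0.996 | 0.994 |

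**2. Observed power as a function of p.** For a two-sided z-test, let z_p = Φ⁻¹(1 - p/2). Then

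observed power = Φ(z_p - 1.96) + Φ(-z_p - 1.96).

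| p | z_p | Observed power |
|---|---|---|
| 0.20 | 1.282 | 25% |
| 0.10 | 1.645 | 38% |
| 0.05 | 1.960 | 50% |
| 0.01 | 2.576 | 73% |
| 0.005 | 2.807 | 80% |
| 0.001 | 3.291 | 91% |

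Sample size does not enter once p is known. For two proportions the relation is nearly the same whatever the event rates. At 62 per group, 17 vs 5 and 24 vs 10 events both give p=0.0048 and observed power 0.813; 25 vs 15 gives p=0.0547 and 0.484. At 70 per group, 31 vs 20 gives p=0.0534 and 0.489. Agreement with the z-test formula is within about 1 to 2 points.

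**3. Two hypothetical results** (chi-square without continuity correction, Wald interval).

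*(a) 62 per group, 16 vs 10 events.* Difference = 16/62 - 10/62 = 9.7 points. SE under the null 0.0731, so z = 0.0968/0.0731 = 1.32 and p=0.186. SE under the alternative 0.0726, so observed power = Φ[(0.0968 - 1.96 × 0.0731)/0.0726] = Φ(-0.64) = 0.26. The 95% CI is 9.7 ± 1.96 × 7.26, that is -4.6 to +23.9 points (Newcombe -4.8 to +23.7).

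*(b) 35 per group, 10 vs 6 events.* Difference = 11.4 points, z = 0.1143/0.1004 = 1.14, p=0.255. Observed power = Φ[(0.1143 - 1.96 × 0.1004)/0.0994] = Φ(-0.83) = 0.20. The 95% CI is -8.1 to +30.9 points (Newcombe -8.4 to +30.2).

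Exact enumeration gives observed power of 0.255 (chi-square) or 0.196 (Fisher) in (a), and 0.199 or 0.136 in (b). In both cases the planned analysis would report 20% to 26% power for a design whose power at the plan's own rates was about 99.7% or 93%. Both intervals exclude the 38-point planning difference.

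**The case against.** The best defence concerns consequence, not substance. No recruitment step, test or decision in the plan depends on the post-hoc figure, so harm requires someone to interpret it wrongly later. That is true and limits the weight of the point. It does not rescue the sentence, because the misinterpretation is written into the plan itself.

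A charitable reading would be power recomputed at the Section 6 rates with the achieved sample. The sentence specifies observed effects, which rules that out. Fisher's test offers no escape: the Fisher p-values of 0.27 and 0.39 in the two examples correspond to 0.197 and 0.137 by the step 2 formula, close to the exact Fisher powers of 0.196 and 0.136.

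It can also be said that group counts and percentages will be reported, so a reader could compute the crude interval, and that silence does not exclude one. This is fair. The missing interval is a gap to fill, not the proof that the sentence is wrong.

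Finally, the event counts are invented, and 38 points is a planning assumption, not a threshold of clinical relevance. Both are right. The examples only illustrate; the table in step 2 carries the argument.

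**Conclusion.** The sentence is wrong as written: the analysis it plans cannot confirm or refute adequacy. Any non-significant result will show about 50% power or less, and 80% will appear only when p is about 0.005 or smaller, whatever the design power was. The mapping is exact for a two-sided z-test at 5% and approximate for chi-square; Fisher's test adds some discreteness. The conclusion is the same whether 70 is the total or the number per group.

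The reach is limited. Data collection, the primary test and the estimates are unaffected; what the report says about adequacy is at risk. This should be corrected before the final analysis, and with data collection planned to August 2026 there is time to do so.

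**What to change.** Delete the sentence from Section 9 and replace it with wording such as:

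> No power will be calculated from observed effects. The crude risk difference (or risk ratio) for PPCs, smokers versus nonsmokers, will be reported with a 95% confidence interval, alongside the adjusted odds ratios and their 95% confidence intervals. Any statement about power will refer to the prospective calculation in Section 6, once its figures have been reconciled.

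The condition at the end matters. On the plan's own rates 90% power corresponds to about 31 per group, so 90% should not be quoted as the design power at 62 per group until Section 6 is settled. The 38-point difference may be cited as the planning assumption, but not as a clinically relevant threshold.

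The cost is a short change to the SAP text. The interval comes from the 2x2 table already needed for the primary test, with no extra data or patients.
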